5.2.2 Timing of Dose Administration

Trial treatment should be administered on Day 1 of each cycle after all procedures/assessments have been completed as detailed on the Trial Flow Chart (Section 6.0). Trial treatment may be administered up to 3 days before or after the scheduled Day 1 of each cycle due to administrative reasons.

All trial treatments will be administered on an outpatient basis.

Pembrolizumab 200 mg will be administered as a 30 minute IV infusion every 3 weeks. Sites should make every effort to target infusion timing to be as close to 30 minutes as possible. However, given the variability of infusion pumps from site to site, a window of -5 minutes and +10 minutes is permitted (i.e., infusion time is 30 minutes: -5 min/+10 min).

The Pharmacy Manual contains specific instructions for the preparation of the pembrolizumab infusion fluid and administration of infusion solution.

5.3 Concomitant Medications/Vaccinations (allowed & prohibited)

Medications or vaccinations specifically prohibited in the exclusion criteria are not allowed during the ongoing trial. If there is a clinical indication for one of these or other medications or vaccinations specifically prohibited during the trial, discontinuation from trial therapy or vaccination may be required. The sponsor-investigator should discuss any questions regarding this with the Merck Clinical team. The final decision on any supportive therapy or vaccination rests with the investigator and/or the subject's primary physician.

5.3.1 Acceptable Concomitant Medications

All treatments that the investigator considers necessary for a subject's welfare may be administered at the discretion of the investigator in keeping with the community standards of medical care. All concomitant medication will be recorded on the case report form (CRF) including all prescription, over-the-counter (OTC), herbal supplements, and IV medications and fluids. If changes occur during the trial period, documentation of drug dosage, frequency, route, and date may also be included on the CRF.

All concomitant medications received within 28 days before the first dose of trial treatment and 30 days after the last dose of trial treatment should be recorded. Concomitant medications administered after 30 days after the last dose of trial treatment should be recorded for SAEs and ECIs as defined in Section 7.2.

5.3.2 Prohibited Concomitant Medications

Subjects are prohibited from receiving the following therapies during the Screening and Treatment Phase (including retreatment for post response/stable disease relapse) of this trial:

- Antineoplastic systemic chemotherapy or biological therapy
- Immunotherapy not specified in this protocol
- Chemotherapy not specified in this protocol
- Investigational agents other than pembrolizumab
- Radiation therapy
- Live vaccines within 30 days prior to the first dose of trial treatment and while participating in the trial. Examples of live vaccines include, but are not limited to, the following: measles, mumps, rubella, varicella/zoster, yellow fever, rabies, BCG, and typhoid vaccine.
- Systemic glucocorticoids for any purpose other than to modulate symptoms from an event of clinical interest of suspected immunologic etiology. The use of physiologic doses of corticosteroids may be approved after consultation with the sponsor-investigator.

Subjects who, in the assessment by the investigator, require the use of any of the aforementioned treatments for clinical management should be removed from the trial. Subjects may receive other medications that the investigator deems to be medically necessary.

The Exclusion Criteria describes other medications which are prohibited in this trial.

There are no prohibited therapies during the Post-Treatment Follow-up Phase.

5.4 Rescue Medications & Supportive Care

5.4.1 Supportive Care Guidelines

Subjects should receive appropriate supportive care measures as deemed necessary by the treating investigator. Suggested supportive care measures for the management of adverse events with potential immunologic etiology are outlined below and in greater detail in the ECI guidance document. Where appropriate, these guidelines include the use of oral or intravenous treatment with corticosteroids as well as additional anti-inflammatory agents if symptoms do not improve with administration of corticosteroids. Note that several courses of steroid tapering may be necessary as symptoms may worsen when the steroid dose is decreased. For each disorder, attempts should be made to rule out other causes such as metastatic disease or bacterial or viral infection, which might require additional supportive care. The treatment guidelines are intended to be applied when the investigator determines the events to be related to pembrolizumab.

Note: if after the evaluation the event is determined not to be related, the investigator is instructed to follow the ECI reporting guidance but does not need to follow the treatment guidance (as outlined in the ECI guidance document). Refer to Section 5.2.1 for dose modification.

It may be necessary to perform conditional procedures such as bronchoscopy, endoscopy, or skin photography as part of evaluation of the event. Suggested conditional procedures, as appropriate, can be found in the ECI guidance document.

- **Pneumonitis:**

- For **Grade 2 events**, treat with systemic corticosteroids. When symptoms improve to Grade 1 or less, steroid taper should be started and continued over no less than 4 weeks.
- For **Grade 3-4 events**, immediately treat with intravenous steroids. Administer additional anti-inflammatory measures, as needed.
- Add prophylactic antibiotics for opportunistic infections in the case of prolonged steroid administration.

- **Diarrhea/Colitis:**

Subjects should be carefully monitored for signs and symptoms of enterocolitis (such as diarrhea, abdominal pain, blood or mucus in stool, with or without fever) and of bowel perforation (such as peritoneal signs and ileus).

- All subjects who experience diarrhea/colitis should be advised to drink liberal quantities of clear fluids. If sufficient oral fluid intake is not feasible, fluid and electrolytes should be substituted via IV infusion. For Grade 2 or higher diarrhea, consider GI consultation and endoscopy to confirm or rule out colitis.
- For **Grade 2 diarrhea/colitis** that persists greater than 3 days, administer oral corticosteroids.
- For **Grade 3 or 4 diarrhea/colitis** that persists > 1 week, treat with intravenous steroids followed by high dose oral steroids.
- When symptoms improve to Grade 1 or less, steroid taper should be started and continued over no less than 4 weeks.

- **Type 1 diabetes mellitus (if new onset, including diabetic ketoacidosis [DKA]) or ≥ Grade 3 Hyperglycemia, if associated with ketosis (ketonuria) or metabolic acidosis (DKA)**

- For **T1DM or Grade 3-4 Hyperglycemia**
 - Insulin replacement therapy is recommended for Type I diabetes mellitus and for Grade 3-4 hyperglycemia associated with metabolic acidosis or ketonuria.
 - Evaluate patients with serum glucose and a metabolic panel, urine ketones, glycosylated hemoglobin, and C-peptide.

- **Hypophysitis:**

- For **Grade 2 events**, treat with corticosteroids. When symptoms improve to Grade 1 or less, steroid taper should be started and continued over no less than 4 weeks. Replacement of appropriate hormones may be required as the steroid dose is tapered.
- For **Grade 3-4 events**, treat with an initial dose of IV corticosteroids followed by oral corticosteroids. When symptoms improve to Grade 1 or less, steroid taper

should be started and continued over no less than 4 weeks. Replacement of appropriate hormones may be required as the steroid dose is tapered.

- **Hyperthyroidism or Hypothyroidism:**

Thyroid disorders can occur at any time during treatment. Monitor patients for changes in thyroid function (at the start of treatment, periodically during treatment, and as indicated based on clinical evaluation) and for clinical signs and symptoms of thyroid disorders.

- **Grade 2** hyperthyroidism events (and **Grade 2-4** hypothyroidism):

- In hyperthyroidism, non-selective beta-blockers (e.g. propranolol) are suggested as initial therapy.
 - In hypothyroidism, thyroid hormone replacement therapy, with levothyroxine or liothyroinine, is indicated per standard of care.

- **Grade 3-4** hyperthyroidism

- Treat with an initial dose of IV corticosteroid followed by oral corticosteroids. When symptoms improve to Grade 1 or less, steroid taper should be started and continued over no less than 4 weeks. Replacement of appropriate hormones may be required as the steroid dose is tapered.

- **Hepatic:**

- For **Grade 2** events, monitor liver function tests more frequently until returned to baseline values (consider weekly).
 - Treat with IV or oral corticosteroids
 - For **Grade 3-4** events, treat with intravenous corticosteroids for 24 to 48 hours.
 - When symptoms improve to Grade 1 or less, a steroid taper should be started and continued over no less than 4 weeks.

- **Renal Failure or Nephritis:**

- For **Grade 2** events, treat with corticosteroids.
 - For **Grade 3-4** events, treat with systemic corticosteroids.
 - When symptoms improve to Grade 1 or less, steroid taper should be started and continued over no less than 4 weeks.

- **Management of Infusion Reactions:** Signs and symptoms usually develop during or shortly after drug infusion and generally resolve completely within 24 hours of completion of infusion. Table 4 below shows treatment guidelines for subjects who experience an infusion reaction associated with administration of pembrolizumab.

Table 4 Infusion Reaction Treatment Guidelines

NCI CTCAE Grade	Treatment	Premedication at subsequent dosing
Grade 1 Mild reaction; infusion interruption not indicated; intervention not indicated	Increase monitoring of vital signs as medically indicated until the subject is deemed medically stable in the opinion of the investigator.	None
Grade 2 Requires infusion interruption but responds promptly to symptomatic treatment (e.g., antihistamines, NSAIDS, narcotics, IV fluids); prophylactic medications indicated for <=24 hrs	
Stop Infusion and monitor symptoms. Additional appropriate medical therapy may include but is not limited to:
 
IV fluids Antihistamines NSAIDs Acetaminophen Narcotics Increase monitoring of vital signs as medically indicated until the participant is deemed medically stable in the opinion of the investigator. If symptoms resolve within 1 hour of stopping drug infusion, the infusion may be restarted at 50% of the original infusion rate (e.g. from 100 mL/hr to 50 mL/hr). Otherwise dosing will be held until symptoms resolve and the participant should be premedicated for the next scheduled dose.
 
Subjects who develop Grade 2 toxicity despite adequate premedication should be permanently discontinued from further trial treatment administration.
	Subject may be premedicated 1.5h (\pm 30 minutes) prior to infusion of pembrolizumab (PEMBROLIZUMAB) with: Diphenhydramine 50 mg po (or equivalent dose of antihistamine). Acetaminophen 500-1000 mg po (or equivalent dose of antipyretic).
Grades 3 or 4 Grade 3: Prolonged (i.e., not rapidly responsive to symptomatic medication and/or brief interruption of infusion); recurrence of symptoms following initial improvement; hospitalization indicated for other clinical sequelae (e.g., renal impairment, pulmonary infiltrates) Grade 4: Life-threatening; pressor or ventilatory support indicated	
Stop Infusion. Additional appropriate medical therapy may include but is not limited to:
 
IV fluids Antihistamines NSAIDs Acetaminophen Narcotics Oxygen Pressors Corticosteroids Epinephrine**
 
Increase monitoring of vital signs as medically indicated until the subject is deemed medically stable in the opinion of the investigator. Hospitalization may be indicated. **In cases of anaphylaxis, epinephrine should be used immediately.
 
Subject is permanently discontinued from further trial treatment administration.
	No subsequent dosing

Appropriate resuscitation equipment should be available in the room and a physician readily available during the period of drug administration.

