5.2.1.2 Dose Modification

Adverse events (both non-serious and serious) associated with pembrolizumab exposure may represent an immunologic etiology. These adverse events may occur shortly after the first dose or several months after the last dose of treatment. Pembrolizumab must be withheld for drug-related toxicities and severe or life-threatening AEs as per Table 3 below. See Section 5.6.1 and Events of Clinical Interest Guidance Document for supportive care guidelines, including use of corticosteroids.

Table 3
Dose Modification Guidelines for Drug-Related Adverse Events

General instructions:				
Immune-related AEs	Toxicity grade or conditions (CTCAEv4.0)	Action taken to pembrolizumab	irAE management with corticosteroid and/or other therapies	Monitor and follow-up
Pneumonitis	Grade 2	Withhold	
 Administer corticosteroids (initial dose of 1-2 mg/kg prednisone or equivalent) followed by taper Add prophylactic antibiotics for opportunistic infections 	
 Monitor participants for signs and symptoms of pneumonitis Evaluate participants with suspected pneumonitis with radiographic imaging and initiate corticosteroid treatment
	Grade 3 or 4, or recurrent Grade 2	Permanently discontinue		
Diarrhea / Colitis	Grade 2 or 3	Withhold	
 Administer corticosteroids (initial dose of 1-2 mg/kg prednisone or equivalent) followed by taper 	
 Monitor participants for signs and symptoms of enterocolitis (ie, diarrhea, abdominal pain, blood or mucus in stool with or without fever) and of bowel perforation (ie, peritoneal signs and ileus).

	Grade 4 or recurrent Grade 3	Permanently discontinue		
 Participants with \geq Grade 2 diarrhea suspecting colitis should consider GI consultation and performing endoscopy to rule out colitis. Participants with diarrhea/colitis should be advised to drink liberal quantities of clear fluids. If sufficient oral fluid intake is not feasible, fluid and electrolytes should be substituted via IV infusion.
AST / ALT elevation or Increased bilirubin	Grade 2 ^a	Withhold	
 Administer corticosteroids (initial dose of 0.5- 1 mg/kg prednisone or equivalent) followed by taper 	
 Monitor with liver function tests (consider weekly or more frequently until liver enzyme value returned to baseline or is stable

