5.6 Subject Withdrawal/Discontinuation Criteria

Subjects may withdraw consent at any time for any reason or be dropped from the trial at the discretion of the investigator should any untoward effect occur. In addition, a subject may be withdrawn by the investigator if enrollment into the trial is inappropriate, the trial plan is violated, or for administrative and/or other safety reasons. Subjects who require cessation of study therapy but do not withdraw consent may remain in standard follow-up for up to 5 years.

A subject must be discontinued from the trial for any of the following reasons:

- The subject or legal representative (such as a parent or legal guardian) withdraws consent.
- Confirmed radiographic disease progression
- Unacceptable adverse experiences as described in Section 5
- Intercurrent illness that prevents further administration of treatment
- Investigator's decision to withdraw the subject
- The subject has a confirmed positive serum pregnancy test
- Noncompliance with trial treatment or procedure requirements
- The subject is lost to follow-up
- Administrative reasons

The End of Treatment and Follow-up visit procedures are listed in Section 6 (Protocol Flow Chart) and Section 7.1.5 (Visit Requirements). After the end of treatment, each subject will be followed for 30 days for adverse event monitoring (serious adverse events may be collected for 90 days after the end of treatment as described in Section 7.2.3.1). Patients may have post-treatment follow-up for disease status up to 5 years at longest, or until disease progression, initiating a non-study cancer treatment, withdrawing consent, or becoming lost to follow-up.

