- If IV steroids followed by high dose oral steroids does not reduce initial symptoms within 48 to 72 hours, treat with additional anti-inflammatory measures. Discontinue additional anti-inflammatory measures upon symptom relief and initiate a prolonged steroid taper over 45 to 60 days. If symptoms worsen during steroid reduction, initiate a retapering of steroids starting at a higher dose of 80 or 100 mg followed by a more prolonged taper and administer additional anti-inflammatory measures, as

needed

- Add prophylactic antibiotics for opportunistic infections.

3.2 *Colitis*

The following AE terms, if considered \geq Grade 2 or resulting in dose modification or use of systemic steroids to treat the AE, are considered ECIs and should be reported to the Sponsor within 2 business days of the event:

- Colitis
- Colitis microscopic
- Enterocolitis
- Enterocolitis hemorrhagic
- Gastrointestinal perforation
- Intestinal obstruction
- Necrotizing colitis
- Diarrhea

All attempts should be made to rule out other causes such as metastatic disease, bacterial or parasitic infection, viral gastroenteritis, or the first manifestation of an inflammatory bowel disease by examination for stool leukocytes, stool cultures, a Clostridium difficile titer and endoscopy. However, the AE should be reported regardless of etiology.

Course of Action

Grade 2 Diarrhea/Colitis (4-6 stools/day over baseline, dehydration requiring IV fluids < 2 business days, abdominal pain, mucus or blood in stool):

- Report as ECI
- Hold pembrolizumab.
- Symptomatic Treatment
- For Grade 2 diarrhea that persists for greater than 3 days, and for diarrhea with blood and/or mucus,
- Consider GI consultation and endoscopy to confirm or rule out colitis
- Administer oral corticosteroids (prednisone 1-2 mg/kg QD or equivalent)
- When symptoms improve to Grade 1 or less, steroid taper should be started and continued over no less than 4 weeks.
- Permanently discontinue for inability to reduce corticosteroid dose to 10 mg or less of prednisone or equivalent per day within 12 weeks.
- If symptoms worsen or persist > 3 days treat as Grade 3

Grade 3 Diarrhea/Colitis (or Grade 2 diarrhea that persists for > 1 week):

- Report as ECI

- Hold pembrolizumab.
- Rule out bowel perforation. Imaging with plain films or CT can be useful.
- Recommend consultation with Gastroenterologist and confirmation biopsy with endoscopy.

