- Treat with intravenous steroids (methylprednisolone 125 mg) followed by high dose oral steroids (prednisone 1 to 2 mg/kg once per day or dexamethasone 4 mg every 4 hours) When symptoms improve to Grade 1 or less, steroid taper should be started and continued over no less than 4 weeks. Taper over 6 to 8 weeks in patients with diffuse and severe ulceration and/or bleeding.
- Permanently discontinue for inability to reduce corticosteroid dose to 10 mg or less of prednisone or equivalent per day within 12 weeks.
- If IV steroids followed by high dose oral steroids does not reduce initial symptoms within 48 to 72 hours, consider treatment with additional anti-inflammatory measures as described in the literature [5]. Discontinue additional anti-inflammatory measures upon symptom relief and initiate a prolonged steroid taper over 45 to 60 days. If symptoms worsen during steroid reduction, initiate a retapering of steroids starting at a higher dose of 80 or 100 mg followed by a more prolonged taper and administer additional anti-inflammatory measures as needed.

Grade 4 events:

- Report as ECI
- Permanently discontinue pembrolizumab.
- Manage as per Grade 3.

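### Section 5.4.1 triggers intravenous steroids for Grade 3 or 4 diarrhea/colitis only after more than a week's persistence; the ECI guidance sets no wait

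*Combined protocol and SAP*

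**What the plan says.** Section 5.4.1 (Supportive Care Guidelines) has two steroid triggers under Diarrhea/Colitis. A Grade 2 event that lasts more than 3 days gets oral corticosteroids. The next bullet covers Grade 3 or 4 and concerns an event "that persists > 1 week, treat with intravenous steroids followed by high dose oral steroids".

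The ECI guidance (Appendix 11.5, section 3.2 Colitis) opens its Grade 3 block with "Grade 3 Diarrhea/Colitis (or Grade 2 diarrhea that persists for > 1 week" and a closing bracket. One instruction in that block is "Treat with intravenous steroids (methylprednisolone 125 mg) followed by high dose oral steroids". For Grade 4 it stops pembrolizumab permanently and adds "Manage as per Grade 3".

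Table 3 in Section 5.2.1.2 has, beside its Grade 2 or 3 diarrhea/colitis row, "Administer corticosteroids (initial dose of 1-2 mg/kg prednisone or equivalent) followed by taper". No duration and no route are given there.

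On where to look for guidance, Section 5.2.1.2 says "See Section 5.6.1 and Events of Clinical Interest Guidance Document for supportive care guidelines, including use of corticosteroids". There is no Section 5.6.1 in the current text; the section with that parent number is "5.6 Subject Withdrawal/Discontinuation Criteria". Sections 5.4.1, 7.1.2.1 and 7.2.3.2 also refer the investigator to the ECI guidance. The overview of that guidance (11.9.1) in turn tells the reader to follow the protocol's own language on dose modification and other treatment options.

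**The concern.** Within 5.4.1 the order is reversed: the severe and life-threatening grades wait longer for their stated steroid treatment than the moderate grade does. Section 5.4.1 presents itself as an outline of what the ECI guidance sets out in more detail, so the two should agree, and on this item they do not.

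What is at stake is a possible delay in treating a patient with severe immune-related colitis. An investigator who takes the 5.4.1 bullet at its word would hold back intravenous steroids for more than a week, in an event for which the ECI guidance gives them without a waiting period.

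**Working it through.** The plan states no figure to reproduce here. The check is a comparison of the texts.

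| Text | Grade 2 | Grade 3 | Grade 4 |
|---|---|---|---|
| Section 5.4.1 | oral steroids after > 3 days | intravenous after > 1 week | intravenous after > 1 week |
| ECI guidance 3.2 | oral steroids after > 3 days, or with blood or mucus; moved to Grade 3 management if prolonged | intravenous, no wait | as Grade 3, so no wait |
| Table 3 | corticosteroids, no wait, route not stated | same row as Grade 2 | no separate steroid entry in the text as read; this may be a merged cell |

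1. *Where the one-week condition belongs.* In ECI 3.2 it sits inside the bracket of the Grade 3 heading and qualifies Grade 2 diarrhea only. Grade 3 enters that block at any duration. In 5.4.1 the same length of time is attached to Grades 3 and 4.

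2. *Size of the discrepancy.* The stated trigger for intravenous steroids is more than 7 days in 5.4.1 and 0 days in ECI 3.2. For scale, ECI 3.2 says to consider further anti-inflammatory treatment if steroids have not reduced the initial symptoms within 48 to 72 hours, which is 2 to 3 days. Under ECI 3.2 that second-line decision can arise before the first-line trigger in 5.4.1 has been met.

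3. *Comparison within 5.4.1.* Six organ headings carry a Grade 3-4 corticosteroid instruction: pneumonitis, diarrhea/colitis, hypophysitis, hyperthyroidism, hepatic and renal. Five have no waiting period, and pneumonitis calls for immediate treatment. Diarrhea/colitis is the only one of the six with a wait. The organs differ and the renal bullet says systemic rather than intravenous, so this is supporting evidence only.

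4. *Whether the cross-references settle it.* Sections 5.2.1.2, 5.4.1, 7.1.2.1 and 7.2.3.2 all point to the ECI guidance. The ECI overview points treatment options back to the protocol. The protocol's language includes both Table 3, which has no wait, and the 5.4.1 bullet, which has one. No sentence states which text prevails.

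5. *A neighbouring inconsistency.* ECI 3.2 has two thresholds for moving Grade 2 to Grade 3 management: more than 1 week in the heading above, and also "If symptoms worsen or persist > 3 days treat as Grade 3". This concerns Grade 2 alone and does not change the comparison for Grades 3 and 4.

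**The case against.** The strongest reply is that little in practice turns on this bullet. Section 5.4.1 calls its measures suggested. Section 5.3 leaves the final decision on supportive therapy with the investigator or the subject's primary physician, and the ECI overview asks for individual clinical judgment. Section 5.3.2 exempts from its steroid prohibition their use for an ECI of suspected immunologic origin, and diarrhea or colitis of Grade 2 or higher is listed as an ECI. Table 3 already gives corticosteroids for Grade 3 without a wait, so for that grade the conflict is mainly about intravenous route and timing. Four sections send the reader to the ECI guidance.

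All of this stands, and it makes a delay less likely. It does not remove the conflict: the printed trigger is still more than a week, and the ECI overview gives a literal reader a reason to treat it as the governing text.

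A reader might infer that the protocol prohibits steroids during the first week of severe colitis. It does not. The bullet says what to do once the event has persisted and is silent on the days before, and Section 5.3.2 and Table 3 allow or direct steroids in that time.

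A reader might also try to count the patients harmed. Section 8.2 cites a rate of about 10% for Grade 3 or higher immune-related events in other studies, and 33 × 0.10 = 3.3 patients across all organs. The documents give neither the share that would be colitis nor the chance that a physician would follow the bullet against Table 3 and ECI 3.2. Any figure built on this would count possible cases, not delayed ones.

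Finally, the description of Grade 4 in Table 6 as calling for urgent intervention is a general grading definition. It does not specify intravenous steroids and adds little.

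**Conclusion.** The inconsistency is real, lies in current text, and should be fixed. Section 5.4.1 sets more than a week's persistence as the trigger for intravenous steroids in Grade 3 or 4 diarrhea/colitis; ECI 3.2 sets none and keeps that condition for Grade 2. Read literally, the bullet could delay first-line intravenous treatment of a severe event by a week.

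That conclusion rests on the wording alone and needs no assumed event rate. How often a delay would occur cannot be derived from the documents, and discretion, Table 3 and the ECI guidance all reduce the likelihood. The stale reference to Section 5.6.1 is a separate editorial slip; it matters here only because it fails to direct the reader to the right text. The efficacy analysis, power, toxicity suspension rules and planned analyses are unaffected.

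**What to change.** In Section 5.4.1, Diarrhea/Colitis, Grade 3 or 4 bullet, delete the persistence condition, that is, the words before the comma in the bullet text quoted above. Leave the rest unchanged, so that the bullet goes directly from naming the Grade 3 or 4 event to the instruction for intravenous and then high-dose oral steroids. This brings it into line with ECI 3.2 for Grades 3 and 4 and conflicts with nothing in Table 3. It is a clinical instruction, so it needs the sponsor's clinical sign-off.

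The deletion does not resolve the two Grade 2 thresholds in ECI 3.2 or the reference to Section 5.6.1. Both could be corrected in the same amendment.

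Cost: one wording amendment and a notice to sites. Sample size, power, suspension thresholds and analysis do not change.
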